Appendix 1: Schedule of Assessments83
Appendix 2: Schedule of Laboratory Tests91
Appendix 3: Adult CFQ-R (English).....99

LIST OF ABBREVIATIONS AND DEFINITIONS OF TERMS

| Abbreviation or Term | Definition/Explanation |
|-----------------------------|--------------------------------------------------------------------------------------------------------------------------------------------------------------------------------------------------------------|
| ADL | Activities of Daily Living |
| AE | Adverse Event |
| ALT (SGPT) | Alanine aminotransferase (Serum Glutamic Pyruvic Transaminase) |
| ANOVA | Analysis of Variance |
| AON | Antisense Oligonucleotide |
| AST (SGOT) | Aspartate aminotransferase (Serum Glutamic Oxaloacetic Transaminase) |
| ATP | Adenosine triphosphate |
| ATS | American Thoracic Society |
| AUC | Area Under the Curve |
| AUC _{0-∞} | Area under the curve from time zero to infinity |
| AUC _{0-t} | Area under the curve from time zero to the final time point |
| bpm | Beats per minute; Breaths per minute |
| bps | Base pairs |
| BUN | Blood Urea Nitrogen |
| C | Celsius |
| CBC | Complete Blood Count |
| CF | Cystic Fibrosis |
| CFR | Code of Federal Regulations |
| CFQ-R | Cystic Fibrosis Questionnaire-Revised |
| CFQ-R RSS | Cystic Fibrosis Questionnaire-Revised Respiratory Symptoms Score |
| CFTR | Cystic Fibrosis Transmembrane Conductance Regulator |
| CH50 | Total Complement |
| CL | Serum Clearance |
| Clinically significant | An abnormal finding/laboratory value that indicates a new disease process, an exacerbation or worsening of an existing condition, or requires further action(s) to be taken (eg, initiation of new therapy). |
| C _{max} | Maximum Concentration |
| C _{min} | Minimum Concentration |
| CRF, eCRF | Case Report Form, Electronic Case Report Form |
| CRO | Contract Research Organization |
| CRP | C-reactive protein |
| CSR | Clinical Study Report |

| Abbreviation or Term | Definition/Explanation |
|-----------------------------|---------------------------------------------------------------|
| CTCAE | Common Terminology Criteria for Adverse Events |
| CXR | Chest Xray |
| DAT | Direct Antiglobulin Test |
| dL | Deciliter |
| DLT | Dose-Limiting Toxicity |
| DP | Drug Product |
| DS | Drug Substance |
| DSMC | Data Safety Monitoring Committee |
| EC, IEC | Ethics Committee, Independent Ethics Committee |
| ECG | Electrocardiogram |
| EMA | European Medicines Agency |
| ENaC | Epithelial Sodium Channel |

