4.0 STUDY OVERVIEW

4.1 Criteria for Evaluation

4.1.1 Primary Endpoint

- Incidence and severity of adverse events (AEs) from baseline through end of study
- Occurrence of dose-limiting toxicities (DLT) in each dose cohort from baseline through end of study

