5.4 Exclusion Criteria

1. Personal or family history of prolonged QT syndrome; or a QTc interval > 430 msec (males) or > 450 msec (females) using Bazett's formula (QTcB)
2. Change in body weight within 90 days prior to Day 1 that is considered clinically significant by the Investigator
3. Abnormal vital signs at screening: heart rate > 120 bpm at rest; systolic blood pressure > 140 or < 90 mmHg; respiration rate > 24 bpm; and SpO₂ < 92% at rest
4. History of alcohol abuse within the past 24 months or positive drug test at screening. Presence of drug(s) administered for known conditions are permitted with concurrence from the Sponsor's Medical Monitor (eg, benzodiazepine, oral cannabis).
5. Any infection including acute upper respiratory or lower respiratory infections, pulmonary exacerbation, changes in therapy for pulmonary disease, or any non

CF-related illness which results in the initiation of any new therapy within 30 days prior to Day 1

6. Clinically significant, abnormal screening laboratory value (as determined by the Investigator) or any abnormal screening laboratory value that would place the subject at undue risk while participating in the study (as determined by the Investigator with concurrence from the Sponsor's Medical Monitor)
7. Breast-feeding or pregnant female
8. Significant change in maintenance medications for CF within 30 days of Day 1
9. Use of lumacaftor or ivacaftor within 45 days of Day 1
10. Use of any investigational drug (other than QR-010) or device within 30 days of Day 1
11. Unable to or unwilling to perform key safety evaluations such as spirometry
12. Unable to participate in standardized airway clearance techniques
13. Presence or medical history of clinically significant disease which precludes study participation or prevents determination of outcome measures
14. History of lung transplantation
15. Hemoptysis of greater than 30 mLs within 90 days prior to Day 1, or hospitalization for hemoptysis within 6 months of Day 1
16. Any severe, acute, or chronic medical or psychiatric condition, laboratory abnormality, or other condition that, in the judgment of the Investigator, would place the subject at undue risk, interfere with the results of the study or make the subject otherwise unsuitable
17. Any difficulty complying with protocol requirements that may increase the risk associated with study participation or study drug administration or may interfere with safety

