5.5 Study Completion and Discontinuation Criteria

5.5.1 Study Completion/Withdrawal

A subject will have the right to withdraw from the study at any time for any reason.

A subject will be discontinued from the study by the Investigator if unacceptable toxicity or withdrawal of consent occurs.

Subjects participating in a MAD cohort that is determined to be greater than the MTD based on dose escalation rules can opt to continue in the study at the next lower dose cohort (ie, at the MTD).

Subjects withdrawn from SAD cohorts should have all assessments conducted at the End of Study Visit at the time of withdrawal. Subjects withdrawn from MAD cohorts should have all

assessments conducted at the End of Treatment Visit as well as the End of Study Visit, for safety monitoring purposes.

Subjects who have completed a SAD cohort are eligible to participate in a MAD cohort, provided there is at least 90 days between the dose in the SAD cohort and the first dose in the MAD cohort.

Allergic reactions may include local dermatitis, angioedema, throat constriction, or anaphylaxis. Appropriate treatment may include administration of antihistamines, hydrocortisone, or epinephrine at the discretion of the assessing physician. Subjects diagnosed with a systemic allergic reaction requiring therapy will be withdrawn from the study.

Given the proposed mechanism of action of QR-010, it could be anticipated that subjects could experience a change in baseline cough, change in sputum quality, or change in sputum volume. A pulmonary exacerbation should be considered if these symptoms are accompanied by fever, body weight loss, generalized malaise. If a pulmonary exacerbation is diagnosed, appropriate interventions including appropriate additional antibiotics should be prescribed by the Investigator or treating physician. Subjects diagnosed with a pulmonary exacerbation requiring the addition of antibiotics will be withdrawn from the study.

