6.4 Adverse Reaction Management

AEs in the study will be treated with appropriate therapies. Acute bronchospasm (defined as a $\geq 15\%$ decrease in FEV₁ % predicted) should be treated with treatment cessation and with β_2 agonists, IV hydrocortisone (100 mg), or other agents as appropriate. Additional supportive care should be provided as necessary by qualified staff with emergency resuscitation equipment.

A Grade 4 (as defined by Common Terminology Criteria for Adverse Events [NCI CTCAE Version 4.03] Modified for CF) adverse reaction requires permanent discontinuation of study drug.

If Grade 2-3 toxicity is noted during the dose administration, the administration should be halted and the subject assessed. If the adverse reaction symptoms resolve promptly, then study drug

administration may be re-initiated. Any Grade ≥ 2 adverse reaction suspected of being related to study drug will result in study drug discontinuation.

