7.4.12 Follow-up Visits—7 and 28 Days After Last Dose

Follow-up visits will occur 7 and 28 days after the last dose of study drug (dose 12).

If at any time during the study the subject discontinues the study early, the subject should return to the clinic to complete the End of Treatment Visit procedures below, and should also return to the clinic to complete the End of Study Visit procedures 28 days after the last study drug dose.

7.4.12.1 7 Days After Last Dose—End of Treatment Visit

1. Subject self-completes the CFQ-R prior to all other procedures and assessments
2. Complete physical examination (including body weight)
3. Vital signs
4. Oximetry
5. Concomitant medication review
6. AE review
7. Chest Xray
8. 12-lead ECG
9. Spirometry
10. Obtain blood and urine samples for local laboratory assessments
11. Obtain urine or blood for pregnancy test (for women of child-bearing potential)
12. Obtain blood samples for PK
13. Obtain sputum sample for the following local laboratory assessment:
 - Microbiology organism identification
14. Obtain blood and sputum samples for inflammatory biomarkers
15. Obtain sample for sweat chloride determination

7.4.12.2 28 Days After Last Dose—End of Study Visit

1. Subject self-completes the CFQ-R prior to all other procedures and assessments
2. Complete physical examination (including body weight)
3. Vital signs
4. Oximetry
5. Concomitant medication review
6. AE review
7. Spirometry
8. Obtain blood and urine samples for local laboratory assessments
9. Obtain urine or blood for pregnancy test (for women of child-bearing potential)
10. Obtain blood and sputum samples for inflammatory biomarkers

11. Obtain serum samples for PK
12. Obtain sample for sweat chloride determination

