12.4.1 Adverse Event Reporting Period

All significant medical conditions including signs/symptoms of the underlying diagnosis found during the screening period and up to randomization will be captured as medical history. Any event/condition related to participation in the trial but not related to underlying or concomitant disease that is noted after screening up to the randomization date will be captured as a non-treatment emergent AE.

Any event/condition noted once the subject is randomized will be captured as an AE. All AEs and SAEs regardless of attribution will be collected until at least 30 days following the last administration of study treatment or initiation of new therapy, whichever is earlier. At the last scheduled visit, the Investigator should instruct each subject to report to the Investigator any subsequent SAEs that the subject's personal physician believes could be related to prior study treatment. Any related non-serious AE occurring after the reporting period may be reported at the discretion of the Investigator.

AEs and SAEs related to study drug that persist >30 days after the last study drug dose should be followed until resolution or until they return to baseline, stabilize, the subject is lost to follow-up, or it has been determined that the study treatment or participation is not the cause of the AE/SAE. Resolution of AEs and SAEs (with dates) should be documented on the AE CRF and SAE form (if applicable) and in the subject's medical record to facilitate source data verification. For some SAEs, the Sponsor or its designee may follow up by telephone, facsimile, electronic mail, and/or a monitoring visit to obtain additional case details deemed necessary to appropriately evaluate the SAE report (eg, hospital discharge summary, consultant report, or autopsy report).

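### Starting any new therapy can end the mandatory AE and SAE collection period before the end-of-study window of both primary endpoints, contradicting Sections 4.1.1, 8.1 and the visit schedule

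*Protocol*

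**What the plan says.** Protocol Section 12.4.1 has AEs and SAEs collected, whatever their attribution, "until at least 30 days following the last administration of study treatment or initiation of new therapy, whichever is earlier". Section 4.1.1 defines both primary endpoints over a longer window: "Incidence and severity of adverse events (AEs) from baseline through end of study" and "Occurrence of dose-limiting toxicities (DLT) in each dose cohort from baseline through end of study". Section 8.1 has AE information captured for the whole study. AE review is listed at the scheduled clinical visits up to Day 8 in SAD and Day 54 in MAD. Under Section 7.4.12 a MAD subject who stops early completes the End of Treatment procedures and "should also return to the clinic to complete the End of Study Visit procedures 28 days after the last study drug dose"; both visits include AE review.

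Section 12.4.1 does not define new therapy or restrict it to another CF or investigational drug. The phrase appears twice elsewhere. In the list of abbreviations, a clinically significant abnormality is one that, among other things, "requires further action(s) to be taken (eg, initiation of new therapy". Exclusion criterion 5 (Section 5.4) covers any non "CF-related illness which results in the initiation of any new therapy within 30 days prior to Day 1". Section 6.4 states that "AEs in the study will be treated with appropriate therapies".

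**The concern.** The clause makes the length of mandatory safety collection depend on what happens to the subject. The protocol expects AEs to be treated, and every DLT category in Section 4.4 involves medical intervention. The subjects most likely to meet the new-therapy condition are therefore those who have already had a reaction.

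In a first-in-human study with six active subjects per cohort, Table 3 of the protocol separates its escalation decisions at one versus two affected subjects, and Section 13.1 counts all AEs towards the safety profile unless they are obviously unrelated. An unrecorded later event in a treated subject could therefore matter. The SAP cannot repair this. Its TEAE definition (Section 4.10.1.1) has a start bound and no end bound, so it would keep a late event that was recorded but cannot recover one that was not. With about 20 to 27 centres (Section 5.2 and the synopsis), sites may also read the clause differently.

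**Working it through.** **Inputs.** SAD: one dose on Day 1, End of Study on Day 8 (Protocol Section 7.3.6 and Table A.1-1, 168 h). MAD: dose 12 on Day 26, End of Study 28 days later on Day 54 (SAP Table 5; Protocol Table A.1-6, 1272 h). For a MAD subject who stops early, End of Study is 28 days after that subject's last dose (Section 7.4.12). The 30-day limit is from Section 12.4.1.

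**1. Reproduce the schedule.** MAD: 26 + 28 = Day 54, and (54 − 1) × 24 = 1272 h. SAD: (8 − 1) × 24 = 168 h. Both agree with the protocol.

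**2. The 30-day limb alone.** SAD: 1 + 30 = Day 31, which is 31 − 8 = 23 days past End of Study. MAD: 26 + 30 = Day 56, which is 56 − 54 = 2 days past. This limb covers both endpoint windows, so the whole gap comes from the new-therapy limb.

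**3. Literal reading: the minimum ends on the day new therapy starts.** Let *d* be that day and *L* the day of the last dose. Days of mandatory collection lost before End of Study are 8 − *d* in SAD and (*L* + 28) − *d* in MAD.

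| Case | Calculation | Days lost |
|---|---|---|
| SAD, *d* = 1 | 8 − 1 | 7 |
| SAD, *d* = 4 | 8 − 4 | 4 |
| MAD, dosing stops at the event, *d* = *L* = 1 | 29 − 1 | 28 |
| MAD, *d* = 13, last dose Day 12 | 40 − 13 | 27 |
| MAD, *d* = 12, dosing continues to Day 26 | 54 − 12 | 42 |
| MAD, *d* = 1, dosing continues to Day 26 | 54 − 1 | 53 |

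In the Day 12 case with dosing continued, 8 of the 15 AE review days from Day 1 onward come after the new therapy.

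**4. Which rows are likely.** Treated reactions mostly end dosing. A MAD subject with a DLT is discontinued from study drug (Section 4.3). An exacerbation needing added antibiotics, or a systemic allergic reaction needing therapy, leads to withdrawal (Section 5.5.1). A Grade 2 or higher AE suspected to be related ends study drug (Section 5.5.3.2). For these subjects *L* is close to *d* and the loss is about 28 days. The 42- and 53-day rows need a therapy that triggers none of these rules, such as one for an AE not suspected to be related. The 7-day SAD figure applies to a subject who stays in the study; one withdrawn outright has the End of Study assessments at withdrawal (Section 5.5.1).

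**5. Alternative reading: 30 days after the earlier of last dose and new therapy.** SAD: the minimum is Day 31 against Day 8, so there is no gap. MAD with all doses given: the shortfall is 54 − (*d* + 30) = 24 − *d*, positive for *d* below 24 and at most 23 days at *d* = 1. If dosing stops at the event, *d* + 30 exceeds *d* + 28 and there is no gap.

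**6. What stays covered.** Related AEs and SAEs persisting more than 30 days after the last dose are followed (Section 12.4.1), and possibly related SAEs are reportable at any time after participation (Section 12.7). After the reporting period, a related non-serious AE is reported only at the investigator's discretion (Section 12.4.1). Mandatory recording of deaths regardless of attribution is tied to the same period (Section 12.4.3e). The exposed data are therefore new events after new therapy that are non-serious or not judged related, and deaths that fall outside that period.

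**The case against.** The strongest reply is that Section 12.4.1 sets a minimum. The words at least permit collection to continue, and the same paragraph says that any event noted after randomization is captured as an AE. Section 8.1 and the visit schedule then carry AE review to End of Study, including for early discontinuers. Section 12.4.3c has recurrent and worsening AEs recorded again, and Section 12.7 asks for a form for every SAE whatever its causality. Supportive treatment is called ancillary therapy in Section 6.3.1, so it is an inference that treating an AE counts as new therapy.

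Most of this stands, and it rules out several stronger readings. A reader might infer that AE collection must stop when a new drug starts, or that safety visits are shortened; the text says neither. A reader might infer that 53 days are lost whenever therapy starts on Day 1; for most treated reactions dosing ends and the figure is about 28. A reader might also infer that AE incidence is shown to be understated at the doses that cause reactions. That does not follow: the triggering reaction is already recorded, SAP Section 4.10.1.1 counts each subject once per term, DLTs are adjudicated by the DSMC, and the documents give no rates of new therapy by arm.

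The reply does not remove the conflict. Section 12.4.1 is the section that defines the reporting period. Sections 12.4.3c and 12.7 set no period of their own for collecting all events regardless of attribution. A site that stopped recording new events at the minimum would be following Section 12.4.1 while departing from Sections 4.1.1 and 8.1.

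**Conclusion.** The point holds as an internal contradiction affecting both primary endpoints, and it should be corrected. The mandatory period can end before the endpoint window does. On the literal reading the shortfall is at most 7 days in SAD. In MAD it is at most 28 days when dosing stops at the event, and at most 53 days when therapy starts on Day 1 and dosing continues. On the alternative reading SAD has no shortfall and MAD has at most 23 days. The conflict in MAD survives either reading.

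These are limits on exposure to loss and not estimates of loss. They assume that treating an AE counts as new therapy, which the protocol's other uses of the phrase support but Section 12.4.1 does not state. They also assume that a site treats the minimum as its stop. Any loss would depend on outcome and could differ between QR-010 and placebo, but neither its size nor its direction can be estimated from the documents. Sample size and alpha are not affected.

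**What to change.** In Section 12.4.1 delete the second limb of the clause, that is, everything after the 30-day period. State that AEs and SAEs are collected for every dosed subject through the later of the End of Study Visit or 30 days after the last dose, whatever other treatment is started. For subjects following the full schedule this gives Day 31 in SAD and Day 56 in MAD, which covers both endpoint windows and agrees with Sections 4.1.1, 8.1 and 7.4.12. The death-recording rule in Section 12.4.3e then follows without separate change.

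In the SAP, add a derived flag for AEs that start after the first new therapy, using AE start dates and the concomitant-medication dates already collected, so that these events can be shown separately.

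The cost is one clause, one flag and a little extra AE recording for subjects who start another treatment. Some added events will be confounded by that treatment; the flag separates them. Dosing, the visit schedule and sample size do not change.

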12.4.2 Eliciting Adverse Events

A consistent methodology of non-directive questioning for eliciting AEs at all subject evaluation time points should be adopted. Examples of non-directive questions include:

“How have you felt since your last clinic visit?”

“Have you had any new or changed health problems since you were last here?”

12.4.3 Recording Adverse and Serious Adverse Events

Investigators should use correct medical terminology/concepts when recording AEs or SAEs on the CRF and/or SAE form. Colloquialisms and abbreviations should be avoided. SAEs must also

be recorded on the AE CRF. Only one medical concept should be recorded in the event field on the AE CRF and SAE form (if applicable).

a. Signs and Symptoms versus Diagnosis

Signs and symptoms should be recorded on the AE CRF rather than the unifying diagnosis. The unifying event term or diagnosis should be recorded as the “etiology” in the CRF (if known), and the SAE form, if applicable. For example, jaundice, asterixis, and elevated transaminases should be recorded on the CRF, and “liver failure” should be recorded as the etiology. As another example, cough, rhinitis, and sneezing should be recorded as AEs on the CRF, and record “upper respiratory tract infection” as the etiology. Vague, nonspecific AE terms such as “erythema,” “rash,” or “lump on head” should be avoided and more specific information should be provided, such as “erythematous macule on right leg,” “allergic dermatitis,” and “scalp cyst.”

b. Adverse Events Occurring Secondary to Other Events

In general, AEs occurring secondary to other events (eg, cascade events or clinical sequelae) should also be entered as separate AEs. For example, if severe diarrhea is known to have resulted in dehydration, both diarrhea and dehydration should be entered as AEs on the CRF, and if also serious, on the SAE form.

c. Persistent or Recurrent Adverse Events

A persistent AE is one that extends continuously, without resolution between subject evaluation time points. Such events should only be recorded once in the CRF unless their severity increases. If a persistent AE becomes more severe or occurs more frequently, it should be recorded again on the AE CRF with the increased severity grading.

A recurrent AE is one that occurs and resolves between subject evaluation time points and subsequently recurs. All recurrent AEs should be recorded individually on the AE CRF.

d. Abnormal Laboratory Values

Only clinically significant laboratory abnormalities that require active management will be recorded as AEs on the CRF and SAE form (if applicable). For example, abnormalities that require study drug dose modification, discontinuation of study treatment, more frequent follow-up assessments, further diagnostic investigation, etc.

If the laboratory abnormality can be characterized by a precise clinical term, the clinical term should be recorded as the AE or SAE. For example, an elevated serum potassium level of 7.0 mEq/L should be recorded as “hyperkalemia.”

Observations of the same clinically significant laboratory abnormality from visit to visit should not be repeatedly recorded as AEs on the CRF and SAE form (if applicable), unless their severity, seriousness, or etiology changes.

e. Deaths

All deaths that occur during the protocol-specified AE reporting period (see Section 12.4.1), regardless of attribution, will be recorded on the AE CRF and SAE form and reported to the Sponsor within 24 hours of event knowledge.

When recording a death, the event or condition that caused or contributed to the fatal outcome should be recorded as a single medical concept. For example, if death resulted from respiratory failure, the AE recorded should be “Respiratory Failure”, and the Outcome of the AE would be “Death”. If the cause of death is unknown and cannot be ascertained at the time of reporting, record “unexplained death” on the AE CRF and SAE form.

f. Preexisting Medical Conditions

A preexisting medical condition is one that is present at the start of the study. Such conditions should be recorded on the Medical and Surgical History CRF.

A preexisting medical condition should be recorded as an AE or SAE only if the frequency, severity, or character of the condition worsens during the study. When recording such events on an AE CRF and SAE form (if applicable), it is important to convey the concept that the preexisting condition has changed by including applicable descriptors (eg, “more frequent headaches”).

g. Pulmonary Exacerbation

Given the proposed mechanism of action of QR-010, it could be anticipated that subjects will experience a change in baseline cough, change in sputum quality, or change in sputum volume. A diagnosis of pulmonary exacerbation should be considered if these symptoms are accompanied by fever, body weight loss, generalized malaise. If a pulmonary exacerbation is diagnosed, appropriate interventions including additional antibiotics should be prescribed by the PI or treating physician. Subjects diagnosed with a pulmonary exacerbation requiring the addition of antibiotics will be withdrawn from the study.

h. Hospitalization, Prolonged Hospitalization or Surgery

Any AE that results in hospitalization or prolonged hospitalization should be documented and reported as an SAE unless specifically instructed otherwise in this protocol.

i. Pregnancy

If a female partner of a male subject in the study becomes pregnant while her partner is receiving investigational therapy or within 6 months after the last dose of study, a Pregnancy form should be completed and faxed to the Sponsor’s Drug Safety Department or its designee within 24 hours of learning of the pregnancy, using the fax numbers listed in the Study Manual.

Abortion, whether therapeutic, or spontaneous, will be reported on a Pregnancy Report form and faxed to the Sponsor according to the instructions in the Study Manual. If the abortion meets seriousness criteria (see Section 12.5, Serious Adverse Event Definition), this information will be captured on the AE CRF and SAE form.

Any congenital anomaly/birth defect in a child born to a female subject or to a female partner of a male subject exposed to the investigational product should be recorded and reported as an SAE.

j. Overdose Reporting

Overdoses must be reported to the Sponsor on an AE CRF and an SAE form for tracking purposes and will be considered a protocol violation. Overdose is defined as any study drug dose administered above the intended dose for the cohort assignment. Additional instructions for reporting overdose information will be provided by the Sponsor at the time of notification.

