#### 4.10.1. Adverse Events

##### 4.10.1.1. General Adverse Event Reporting

Adverse events will be summarized with MedDRA System Organ Class (SOC) and Preferred Term, by subject incidence rates, therefore, in any tabulation, a subject contributes only once to the count for a given adverse event (SOC or preferred term or AESI).

A treatment emergent Adverse Event (TEAE) is defined as an event with start date at/or after first dose.

An overall summary of TEAEs will include the number of

- Subjects with at least one TEAE,
- Number of TEAE,
- Subjects with study drug-related TEAEs,
- Subjects with device-related TEAEs,
- Subjects with TEAEs by maximum severity grade,
- Subjects with serious AEs,
- Subjects with TEAEs Leading to Treatment Discontinuation,
- Subjects with TEAEs Leading to Study Discontinuation,
- Deaths

The overall incidence of TEAEs will be summarized by treatment group and classified by SOC and PT. Reporting will include reports for Serious AEs, AEs leading to treatment discontinuation, deaths, AEs related to study drug, AEs related to device. AEs by SOC and PT will be presented by maximum severity.

An AE will be considered drug-related if the Investigator or Sponsor indicated that the event is coded "possibly" or "definitely" related to study drug or if the relationship is missing. The same definition applies for relationship to device.

AE intensity is graded on a 5 level category (Mild/Grade 1, Moderate/Grade 2, Severe/Grade 3, Life threatening/Grade 4, Death/Grade 5). Maximum intensity per PT is reported.

TEAEs will be listed in subject listings. Listings of Serious TEAEs, Death, Grade 2 or higher TEAEs will also be presented.

A listing for the non-treatment emergent events (with start date and time prior to first dose) will be provided, the listing will be provided only if events are collected.

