###### 4.10.1.2.1. AESI1: Atelectasis

Atelectasis is defined as the AEs of at least Grade 2 with the preferred term that contains "atelectasis".

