#### 4.10.1.2.5. AESI5: Pneumonitis

Pneumonitis is defined as the AEs of at least Grade 2 with the preferred term that contains "pneumonitis".

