#### 4.10.1.2.9. AESI9: Allergic Reaction

Allergic Reaction is defined as the AEs of at least Grade 2 with the preferred term that contains "Hypersensitivity" or "Alveolitis" or "vasculitis" or "urticaria" or "dermatitis allergic" or "anaphylactic" or "anaphylaxis".

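### Sites are told to record signs and symptoms rather than the diagnosis, but the SAP finds atelectasis and pneumonitis only by a diagnosis word in the preferred term, so those AESI rows can under-count; the allergic reaction row is partly exposed.

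*Protocol*

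**What the plan says.** Protocol 12.4.3, item a, sets the recording rule: "Signs and symptoms should be recorded on the AE CRF rather than the unifying diagnosis". It continues: "The unifying event term or diagnosis should be recorded as the" etiology in the CRF, if known, and on the SAE form where one applies. One worked example is respiratory: "cough, rhinitis, and sneezing should be recorded as AEs on the CRF", with upper respiratory tract infection entered only as the etiology.

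The SAP works from the coded AE term. Section 4.10.1.1 states: "Adverse events will be summarized with MedDRA System Organ Class (SOC) and Preferred Term, by subject incidence rates". Section 4.10.1.2 then defines nine AESIs. The three that matter here are:

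- AESI1: "Atelectasis is defined as the AEs of at least Grade 2 with the preferred term that contains" the word *atelectasis*.
- AESI5: "Pneumonitis is defined as the AEs of at least Grade 2 with the preferred term that contains" the word *pneumonitis*.
- AESI9: "Allergic Reaction is defined as the AEs of at least Grade 2 with the preferred term that contains" one of seven strings: hypersensitivity, alveolitis, vasculitis, urticaria, dermatitis allergic, anaphylactic, anaphylaxis.

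On allergic reactions, Protocol 5.5.1 says: "Allergic reactions may include local dermatitis, angioedema, throat constriction, or anaphylaxis".

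The SAP does not code, search or otherwise use the etiology field or the SAE-form diagnosis, and SAP section 5 reports no changes from the protocol-defined analyses.

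**The concern.** The collection rule and the search rule point at different fields. A site that follows item a keeps the diagnosis out of the AE term, and the SAP looks for the diagnosis only in that term. A pneumonitis entered as cough, fever and dyspnoea, with pneumonitis as the etiology, is not found by AESI5. The same holds for atelectasis. For allergic reactions there is a further gap that does not depend on the recording rule: two manifestations that the protocol itself calls allergic are not on the search list.

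At stake is whether the AESI summary and AESI listings in the study report can be read at face value. For an inhaled product with no earlier clinical studies, a zero in the pneumonitis row will be taken to mean that no pneumonitis was seen. Here it could also mean that sites diagnosed it and recorded it as they were told. Because the protocol says *should*, practice may differ between sites, so the same event could be counted at one site and missed at another.

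**Working it through.** The documents give no figure on this point, so there is none to reproduce. The check applies the SAP search strings to terms that the documents themselves use.

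**Step 1. Sort the nine AESIs by data source (SAP 4.10.1.2.1 to 4.10.1.2.9).**

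- Laboratory or oximetry data: AESI4 (liver tests) and AESI8 (hypoxia). The recording rule does not touch them.
- Preferred term, but a sign or symptom: AESI2 (hypotension), AESI6 (crackles), AESI7 (dyspnoea). The recording rule favours their capture.
- Preferred term, mixed: AESI3 (bronchospasm, which includes wheezing) and AESI9 (allergic reaction, which includes urticaria).
- Preferred term, diagnosis word only: AESI1 and AESI5.

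So 2 + 3 + 2 + 2 = 9. Seven use the preferred term, but only two can be reached by the diagnosis word alone.

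**Step 2. Run the *contains* search.** The strings for AESI1, 3, 5, 6, 7 and 9 were applied. AESI2 was left out because none of its strings bears on these terms.

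| Term entered as the AE | Where the term comes from | AESI found |
|---|---|---|
| atelectasis | Protocol Table 2 | AESI1 |
| pneumonitis | Protocol Table 2 | AESI5 |
| anaphylaxis | Protocol 5.5.1 | AESI9 |
| dermatitis allergic | SAP AESI9 list | AESI9 |
| urticaria | SAP AESI9 list | AESI9 |
| dyspnoea | Protocol Table 2, as a symptom of atelectasis | AESI7 only |
| cough | Protocol Table 2, as a symptom of atelectasis | none |
| angioedema | Protocol 5.5.1 | none |
| throat constriction | Protocol 5.5.1 | none |
| dermatitis (not called allergic) | Protocol 5.5.1 | none |

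The two symptoms that Protocol Table 2 gives for atelectasis lead to AESI7 or to nothing. AESI7 also requires at least Grade 2 for the dyspnoea itself.

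**Step 3. Size of one missed event.** An unexpanded cohort has 6 active subjects (Protocol 13.2), so one event is 1/6 = 16.7%, and missing it takes that row from 17% to 0%. If a cohort is expanded by four subjects, and if those four are also split 3:1 (an assumption), there are 6 + 3 = 9 active subjects and one event is 1/9 = 11.1%.

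**Step 4. Illustration.** Let p be the true subject-level rate of one AESI and s the probability that a case is found by the search. Both are assumed; neither is in the documents. The chance that the row shows at least one case among 6 active subjects is 1 − (1 − p·s)^6.

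| p | s = 1 | s = 0.5 |
|---|---|---|
| 10% | 1 − 0.90^6 = 0.469 | 1 − 0.95^6 = 0.265 |
| 20% | 1 − 0.80^6 = 0.738 | 1 − 0.90^6 = 0.469 |
| 30% | 1 − 0.70^6 = 0.882 | 1 − 0.85^6 = 0.623 |

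Halving capture has the same effect on the row as halving the true rate.

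**The case against.** There is a good case that this is a small matter, and most of it stands.

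- *The rule is not absolute.* Item a says *should*, and it offers allergic dermatitis as an acceptable AE term. Protocol Table 2 lists atelectasis and pneumonitis by name as AEs of interest, so a site could reasonably enter them as AE terms. This stands: under-counting is possible, not certain. It does not remove the conflict, because the two instructions still differ.
- *Many cases reappear.* Dyspnoea of Grade 2 or higher is AESI7, crackles AESI6, wheezing AESI3, hypotension AESI2, and saturation below 88% AESI8. This stands for the count of subjects with any AESI, which is less affected than the single rows. It is not assured, since cough and fever have no row, and a pneumonitis counted as dyspnoea is still misclassified.
- *Bronchospasm is not hidden.* Protocol 6.4 ties acute bronchospasm to a measured fall in FEV1, AESI3 includes wheezing, and SAP 4.10.1.4 reports FEV1 falls of 15% or more separately. This stands, and bronchospasm is no part of the point.
- *The fix may not be as simple as it looks.* The eCRF and Data Management Plan are cited in SAP 1.1 but are not available here, so it is unknown whether etiology is free text or is linked across signs. This stands as a limit.

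A reader might go further and infer that the primary endpoint or the dose decisions are compromised. The documents do not support that. The SOC and preferred-term tables and the Grade 2 or higher listing (SAP 4.10.1.1) keep every recorded sign at its own grade. DLTs are adjudicated by the DSMC and loaded from a separate file (SAP 4.10.1.3). Grade 2 or higher AEs of interest go to the DSMC as the protocol defines them (SAP 2.5.2), and cohort expansion follows Protocol 4.3 and Table 2. None of these uses the SAP search strings. Nor are the AESI tables the main display of the primary endpoint; they are one safety display among several.

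**Conclusion.** The concern holds for individual AESI rows. If both documents are followed as written, atelectasis and pneumonitis can be missing from their rows or appear under another AESI. Allergic reaction is partly exposed, and its list omits angioedema and throat constriction whatever the sites do. The size is 17 percentage points per missed event in an unexpanded dose group.

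It would be wrong to say that seven of nine AESIs are exposed. Seven depend on the preferred term, but three of those are signs or symptoms and two are partly reachable through a sign.

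The conclusion assumes that sites follow item a at least some of the time, and that no mapping from etiology to AESI exists in a document not available here. How often cases would be missed cannot be estimated from the documents.

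**What to change.** In SAP 4.10.1.2:

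1. Code the CRF etiology entry in MedDRA, together with the SAE-form diagnosis where there is one.
2. Flag an AESI when either the AE preferred term or the coded etiology matches the search list. For the Grade 2 threshold, use the highest grade among the signs linked to that etiology.
3. Add angioedema and throat constriction or tightness to the AESI9 terms, so that the list covers these reactions named in Protocol 5.5.1.

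The cost is SAP wording and the coding of one more field that the protocol already asks sites to complete; no new visit or measurement is needed. AESI counts may rise slightly, and some subjects will appear under two AESIs, for example dyspnoea and pneumonitis, so a footnote should say so. There is no gain where etiology is blank, and the highest grade among the signs may fall below the grade that the diagnosis itself would have received.
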